7.3.3.1 Composite endpoint

The secondary efficacy endpoint, time to progression defined as a composite endpoint will be analyzed using the method described in [Section 7.3.3](#). The composite endpoint is defined by including any of the following events.

- Absolute decline of 10% predicted in FVC (i.e. $FVC \text{ percent predicted}_{\text{baseline}} - FVC \text{ percent predicted}_{\text{progression}} \geq 10\%$)
- Nonelective hospitalization for respiratory events
- Lung transplantation or death

7.3.3.2 Other Time-to-Event endpoints

The time-to-event types secondary efficacy endpoints listed as follows will be applied only by the Kaplan-Meier curve method where number of subjects at risk at each visit and the proportion of subjects who progressed in each treatment group will be summarized and presented.

- Time to first acute exacerbation (using modified diagnostic criteria for acute IPF exacerbation derived from [Collar 2007]), measured in days.
- Time to death or lung transplantation measured in days.
- Time to all nonelective hospitalizations, measured in days.
- Time to all nonelective respiratory hospitalizations, measured in days.

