7.3. Study Stopping Rules

Biogen may terminate this study at any time. Biogen will notify Investigators if the study is to be placed on hold, completed, or terminated.

The DSMB will conduct regular reviews of all safety data in an unblinded format. Following each review, the DSMB will provide a recommendation to Biogen regarding the appropriateness of continuing the study from a safety perspective, as well as any other recommendations relevant to study conduct and/or subject safety.

The DSMB may recommend discontinuing the study if the event rate in the BG00011 treated arm is 20% higher compared with placebo. The events include, but may not be limited to:

- cumulative number of deaths and/or;
- number of lung transplantations and/or;
- cumulative number of subjects with a confirmed absolute decline of % predicted FVC ≥ 15 from baseline.

The meeting intervals and the procedures used to provide and assess the data will be described in detail in the DSMB charter.

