10.2. Withdrawal of Subjects From the Study

Study withdrawal is defined as the premature ending of study visits and assessments. The reasons for mandatory study withdrawal are listed below (Section 10.2.1). Note that discontinuation of study treatment does not require withdrawal from the study if a subject continues to attend clinic visits and complete assessments.

If a subject is withdrawn from the study, an End of Treatment Visit will be scheduled or performed as soon as possible but within 4 weeks. All assessments planned for the Week 52 Visit except the HRCT scan will be performed (see Table 2 for a list of assessments to occur at the End of Treatment Visit).

If a subject is unwilling or unable to attend, at minimum, the End of Treatment Visit, and decides to withdraw consent, the reason for withdrawal will be documented and no further assessments will be obtained.

Subjects who are withdrawn from the study will not be replaced.

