1 INTRODUCTION

The intent of this document is to provide guidance for analyses of data for this Phase 2b study. This statistical analysis plan (SAP) has been developed after review of the Clinical Study Protocol 203PF203 (version 1 dated 20NOV2017).

On 16 August 2019, the BG00011 independent Data Safety and Monitoring Board (DSMB) met for a routinely scheduled bi-monthly meeting. During that meeting the DSMB recommended that study 203PF203 be stopped due to an imbalance in the prespecified safety composite endpoint. A separate unblinded team at Biogen has reviewed the data and accepted the DSMB recommendation. Because of the study early termination, the version 2 protocol dated on 02 JULY 2019 was not implemented, it is not used as reference for developing this SAP.

As the study was stopped early, all endpoints will be analyzed and summarized by descriptive statistics only with exception of primary and key secondary efficacy endpoints (i.e. Percent Predicted FVC, Absolute DLco corrected for hemoglobin and Percent Predicted Absolute DLco corrected for hemoglobin). The safety data will be analyzed in full. This version 1.0 SAP supersedes the statistical considerations identified in the protocol.

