7.3.3 Analysis of Time-to-Event Endpoints

The time-to-event endpoints will be analyzed using survival analyses methods. The Kaplan-Meier curve and number of subjects at risk at each visit will be presented. The proportion of subjects who progressed in each treatment group will be summarized.

Time to event will be analyzed by a cox proportional hazards model with terms for treatment (BG00011 vs. placebo) and randomization stratification factor. A stratified log-rank test will be used to compare the 2 treatment groups using randomization stratus as the stratification factor. The progression will be summarized descriptively for each stratum.

Censoring rules will be applied for all time-to-event endpoints, unless otherwise specified. Subjects who do not experience an event by early termination, will be censored at the date of last assessment during the treatment period. The start date for calculation of day to censor or event will be the date of first dose. If a subject who was not on background therapy at randomization initiate treatment with background therapy during the study, the study will be censored at the time of new background therapy initiation. If a subject who was on background therapy at randomization stop background therapy during the study, the study will be censored at the time of the background therapy stopped.

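### Kaplan-Meier curves for first exacerbation and nonelective hospitalisation censor deaths by default, so 1−KM modestly overstates absolute risk; cumulative incidence should be added beside them

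*SAP*

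**What the plan says.** SAP 7.3.3.2 lists four secondary endpoints: time to first acute exacerbation, to death or lung transplantation, to nonelective hospitalisation of any cause, and to nonelective respiratory hospitalisation. It states: "The time-to-event types secondary efficacy endpoints listed as follows will be applied only by the Kaplan-Meier curve method". Numbers at risk and the proportion of subjects with the event accompany the curves.

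The censoring rule is in SAP 7.3.3. Its scope is general: "Censoring rules will be applied for all time-to-event endpoints, unless otherwise specified". Its content is: "Subjects who do not experience an event by early termination, will be censored at the date of last assessment during the treatment period". The section also censors subjects who start or stop background therapy. It does not mention death or transplantation.

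Elsewhere the SAP does deal with both. In 7.3.3.1, "Lung transplantation or death" is a component of the progression composite. In 7.2.1 they are intercurrent events for FVC. In 7.3.3.2 they form an endpoint of their own. Nothing comparable is given for exacerbation or for the two hospitalisation endpoints, and no readable section plans a cumulative incidence function.

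**The concern.** A subject who dies cannot later have a first exacerbation or a hospitalisation. Kaplan-Meier censoring treats that subject as someone who still could, with the same future risk as those who remain. The complement of the curve, 1−KM, then estimates event risk in a hypothetical setting without death, and it exceeds the proportion of subjects who would actually have the event.

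The context makes this worth stating. SAP section 1 reports that the DSMB "recommended that study 203PF203 be stopped due to an imbalance in the prespecified safety composite endpoint". Protocol 7.3, in version 1 on which the SAP is based, includes among the events that may prompt a stopping recommendation "cumulative number of deaths and/or" and "number of lung transplantations and/or". Unequal mortality between arms is therefore plausible, though not documented. If mortality does differ, the overstatement differs by arm. The crude proportions do not settle the matter, because early termination left subjects with unequal follow-up.

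**Working it through.** **Plan's own figure.** The documents state no event rate, mortality or power for these endpoints, so there is nothing to reproduce here. The one power statement (SAP section 4) concerns FVC: 145 × 0.85 = 123.25 evaluable per arm, a difference of 82.5 mL/year, SD 280 mL and two-sided alpha 0.15 give 80.9%, matching the stated 80% or so. Nothing below depends on it.

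**Inputs.** Method and censoring rule: SAP 7.3.3 and 7.3.3.2. Assumed, because the documents are silent: annual event risk e of 5–30%; annual mortality d of 2–20%; constant hazards; death as the only competing event. One anchor for mortality is the five-year survival of 30% to 50% in Protocol 4.1. At constant hazard this is 1 − 0.50^(1/5) = 12.9% to 1 − 0.30^(1/5) = 21.4% per year. That describes IPF in general, and eligibility criteria may lower it in this trial.

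**Formulas.** With λ1 = −ln(1−e), λ2 = −ln(1−d) and t in years:
- 1−KM(t) = 1 − exp(−λ1·t)
- Cumulative incidence (t) = λ1/(λ1+λ2) × [1 − exp(−(λ1+λ2)·t)]

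**Worked case, e = 20%, d = 10%.** λ1 = 0.2231, λ2 = 0.1054, ratio λ1/(λ1+λ2) = 0.679.
- One year: 1−KM = 20.0%; cumulative incidence = 0.679 × (1 − 0.80 × 0.90) = 0.679 × 0.28 = 19.0%; excess 0.98 points.
- Week 26: 1−KM = 1 − √0.80 = 10.56%; cumulative incidence = 0.679 × (1 − √0.72) = 10.29%; excess 0.27 points.

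**Range.**

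| Annual event risk | Annual mortality | 1−KM, 1 year | Cumulative incidence, 1 year | Excess, points (relative) | Excess at Week 26, points |
|---|---|---|---|---|---|
| 5% | 2% | 5.0% | 4.95% | 0.05 (1.0%) | 0.01 |
| 10% | 5% | 10.0% | 9.75% | 0.25 (2.5%) | 0.06 |
| 10% | 10% | 10.0% | 9.50% | 0.50 (5.3%) | 0.13 |
| 20% | 10% | 20.0% | 19.02% | 0.98 (5.2%) | 0.27 |
| 30% | 20% | 30.0% | 27.07% | 2.93 (10.8%) | 0.85 |

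A simulation with 145 subjects, administrative censoring and 500 runs per setting compared 1−KM with the Aalen-Johansen estimate. At event/death risks of 10/5%, 20/10% and 30/20% it gave 10.0 vs 9.7%, 20.0 vs 19.0% and 30.3 vs 27.3%.

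**Unequal deaths.** Take the same event hazard in both arms (20% per year) and mortality of 15% in one arm and 5% in the other. 1−KM is 20.0% in both. Cumulative incidence is 18.5% and 19.5%, so the excess is 1.5 and 0.5 points.

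**Against sampling error.** With all 145 subjects in an arm followed, the 95% half-width at a 20% risk is 1.96 × √(0.20 × 0.80/145) = 6.5 points. Early stopping makes it wider.

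**The case against.** The strongest reply is that the curves do nothing wrong for one legitimate question. In the unequal-deaths case KM is identical in the two arms, which is correct: the event hazards are equal. Cumulative incidence makes the arm with more deaths look better by a point. In a trial stopped for safety, replacing KM could flatter the worse arm. This stands, and it is why cumulative incidence should be added and not substituted. A reader might infer that the comparison between arms is distorted. For event hazards it is not; only the absolute-risk reading is affected.

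Three other stronger readings are tempting, and the documents do not support them.

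- That the curves are the only analysis of these endpoints. The crude proportions are also planned. Exacerbation has a binary analysis with odds ratio, relative risk and absolute risk reduction (SAP 7.3.2 and 7.3.2.1) and a count summary (7.3.4.1). Respiratory hospitalisation enters the progression composite, where death and transplantation are events (7.3.3.1).
- That transplanted subjects are censored. No text says so. Protocol 10.2 notes that "discontinuation of study treatment does not require withdrawal from the study if a subject continues to attend clinic visits and complete assessments", so a transplanted subject may stay under observation. The gap is an unstated rule.
- That the composite behind the stop contained deaths and transplants. SAP section 1 does not list its components, and Protocol 7.3 lists stopping events without calling them a composite.

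The size is also small against sampling error, and not every death competes: Protocol 4.1 cites 56.2% one-year survival after an exacerbation, so some deaths follow the event. Finally, SAP 7.4 is redacted and the table shells are not available, so further handling there cannot be ruled out.

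**Conclusion.** The point holds as a minor one. For these three endpoints a subject who dies without the event is censored as a consequence of the general rule, though no sentence says so expressly, and the treatment of transplantation is left open. Read as the probability of the event, 1−KM is too high. Across the assumed rates the one-year excess runs from about 0.05 to 2.9 points; at Week 26 it stays under 0.9. It is larger in whichever arm has more deaths. These figures rest on constant hazards and assumed rates, not trial data. Used as a display of the cause-specific hazard, the curves stand. No test is planned on them, and the primary analysis and sample size are unaffected.

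**What to change.** For first exacerbation, all nonelective hospitalisation and nonelective respiratory hospitalisation:

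1. State that death without the event is a competing event, and state a rule for transplantation (competing event, censoring, or continued observation).
2. Keep the KM curves and add Aalen-Johansen cumulative incidence by arm, with 95% CI at Week 26. Give later weeks only where numbers at risk allow: SAP 7.3.1.1 already says the 52-week continuous endpoints lack data.
3. Present these figures next to the planned death-or-transplant curve, so that fewer events because of more deaths are not taken as benefit.

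Dates of death and transplantation are already needed for 7.3.3.1 and 7.3.3.2, so no new data are required. The cost is a software option and three extra figures. One limit remains: censoring at a start or stop of background therapy would still apply to the cumulative incidence curves, so they too would depend on that rule.

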7.3.4 Analysis of Other Endpoints

7.3.4.1 Number of Occurrences

The secondary efficacy endpoint, number of exacerbations during 52 weeks, defined by using the 2007 modified diagnostic criteria [Collard 2007], a listing will be provided if less than 4 subjects in each treatment group in which each subject experiences more than one exacerbation during the study period. If no fewer than 4 subjects in either treatment group in which each subject experience more than one exacerbation during the study period, a table of summary descriptive statistics will be provided with its associated listing.

7.4 Analysis of Exploratory Efficacy Endpoints

[REDACTED]

[REDACTED]

[REDACTED]

[REDACTED]

[REDACTED]

[REDACTED]

[REDACTED]

[REDACTED]

[REDACTED]

[REDACTED]

[REDACTED]

[REDACTED]

[REDACTED]

[REDACTED]

[REDACTED]

[REDACTED]

[REDACTED]

[REDACTED]

[REDACTED]

[REDACTED]

[REDACTED]

[REDACTED]

[REDACTED]

- [REDACTED]

[REDACTED]

- [Redacted]
- [Redacted]
- [Redacted]
- [Redacted]
- [Redacted]

[Redacted]

[Redacted]

[Redacted]

- [Redacted]
- [Redacted]
- [Redacted]
- [Redacted]
- [Redacted]
- [Redacted]

[Redacted]

[Redacted]

[Redacted]

- [Redacted]
- [Redacted]

[Redacted]

[Redacted]

- [Redacted]
- [Redacted]

[Redacted]

[Redacted]

- [Redacted]
- [Redacted]

[Redacted]

[Redacted]

[Redacted]

[Redacted]

- [Redacted]
- [Redacted]
- [Redacted]
- [Redacted]

[Redacted]

- [Redacted]
- [Redacted]

8 Safety Analysis

8.1 General Consideration

All safety analyses will be performed for the safety population unless otherwise specified. No statistical testing will be performed on the safety data.

8.2 Analysis of Adverse Events (AEs)

All AEs will be coded by system organ class and preferred term using the Medical Dictionary for Regulatory Activities (MedDRA) dictionary (Version 22.0). In this study, all AEs will be analyzed based on the principle of treatment emergence. Therefore, whenever an analysis of summary of AEs is mentioned, it is intended that this is in reference to treatment emergence AEs (TEAEs). A TEAE is defined as an AE that has an onset date on or after the date of first dosing, or if it was present prior to the first dose and subsequently worsened until last follow up visit.

To define treatment emergence for AEs with missing start or stop date or time the following additional criteria will be used:

- if both the start and stop dates for an AE are missing, then this AE is considered treatment emergent;
- if the start date for an AE is missing and the stop date/time falls after the first dose date/time, then this AE is considered treatment emergent;
- if the start date for an AE was the same as the first dose date, and the start time was missing, then that event is considered treatment emergent.

For AEs with a partial start date, the year/month of the event date will be compared to that of the first dosing date to determine whether the event is treatment emergent.

Overall TEAE summary table will include the number of subjects with any TEAE, the number of subjects with any TEAE by maximum severity (mild, moderate, severe), the number of subjects with any related TEAE, the number of subjects with Serious adverse events (SAE), the number of subjects with related SAE, the number of subjects with TEAE leading to withdrawal of study drug, the number of subjects with TEAE leading to study withdrawal, and the number of deaths. The overall TEAE summary table will be provided for all subjects in the safety population and for subjects in each randomization stratification factor.

Incidence is defined as the number of subjects who experienced an event and each subject will be counted only once within each category. Therefore, to count the number of subjects who experience TEAEs within each preferred term (PT), a subject experiencing the same TEAE multiple times will only be counted once for that PT. Similarly, if a subject experience multiple TEAEs within the same system organ class (SOC), that subject will be counted only once for that SOC category. For subjects experiencing the same AE more than once within a same SOC and PT, that subject will be counted only once at the maximum severity in the calculation of incidence by severity.

Incidence proportion (i.e. percentage, %) is defined as the number of subjects who experienced an event divided by total number of subjects in the analysis population times 100.

The following incidence tables of TEAEs will be presented. The Incidence and incidence proportion will be provided in the incidence tables. The sorting order for TEAE incidence tables, unless otherwise specified, will be by decreasing frequency order of total column within each category. For the table of TEAEs by SOC and PT sorted by decreasing frequency presented by treatment group, SOCs will be presented in decreasing frequency order of total column, and within each SOC, PTs will be presented in decreasing frequency order of total column.

- TEAEs by SOC and PT sorted by decreasing frequency
- TEAEs by SOC and PT sorted by alphabetical order
- TEAEs at least 5% higher in incidence by SOC and PT for BG00011 compared to placebo
- TEAEs by PT
- TEAEs by PT with an incidence of 5% or more in any treatment group
- Severe TEAEs by SOC and PT
- Severe TEAEs by PT
- TEAEs by maximum severity by SOC and PT
- TEAEs by maximum severity by PT
- Related TEAEs by SOC and PT
- SAE by SOC and PT
- SAE by PT
- Related SAE by SOC and PT
- TEAEs that led to discontinuation of study drug by SOC and PT
- TEAEs that led to withdrawal from study by SOC and PT
- Incidence rates of TEAEs by SOC and PT
- Suspected unexpected serious adverse reactions (SUSAR) by SOC and PT

The following listings will be provided:

- Listing of all TEAEs
- Listing of SAEs
- Listing of TEAEs that led to discontinuation of study drug
- Listing of TEAEs that led to withdrawal from study
- Listing of deaths

8.2.1 Subgroup Analysis of AE

The analysis of AE will be evaluated on pre-defined subgroups which includes:

- Regions (Australia, Asia, Europe, North America, South America)
- Usage of background therapy: Nintedanib or Pirfenidone.

The following incidence tables will be presented by pre-defined subgroups using the same methods as mentioned in [Section 8.2](#).

- SAE by SOC and PT by region
- SAE by PT by region
- SAE by SOC and PT by usage of background therapy
- SAE by PT by usage of background therapy

The region and background therapy (Nintedanib or Pirfenidone) will also be including in the following listings.

- Listing of SAEs
- Listing of AE of exacerbation

8.3 Analysis of Laboratory Tests

The following laboratory safety assessments will be conducted:

- Hematology: complete blood count (CBC) including red blood cell count, white blood cell counts with differentials (neutrophils, lymphocytes, monocytes, eosinophils, and basophils), hemoglobin, hematocrit, mean corpuscular volume (MCV), mean corpuscular hemoglobin (MCH), and mean corpuscular hemoglobin concentration (MCHC).
- Serum chemistry: albumin, alkaline phosphatase, alanine aminotransferase (ALT), aspartate aminotransferase (AST), blood urea nitrogen (BUN), calcium, chloride, carbon dioxide, creatinine, direct bilirubin, gamma-glutamyl transpeptidase, glucose, lactate dehydrogenase (LDH), phosphorus, potassium, sodium, total bilirubin, total protein
- Urinalysis: including urine protein, glucose, ketones, occult blood, and white blood cells by dipstick, with microscopic examination if indicated

The clinical laboratory parameters include safety assessment listed above will be summarized by treatment group and visit. Descriptive statistics will be presented for continuous variables at each visit by treatment group, including number of subjects, mean, standard deviation, median, 25%, 75% quartiles, minimum, and maximum values. Plots of mean value with standard error for numeric laboratory parameters at each visit will be presented. For categorical endpoints, summary statistics will be presented at each visit by treatment group include number and percentage of subjects with data in each category.

Changes from baseline and percent changes from baseline in quantitative laboratory values will be summarized using descriptive statistics by treatment group and visit.

The clinical laboratory parameters by worst post-baseline grade will be provided for all safety assessment. The worst post-baseline cumulative grade will be provided for the safety assessments for Hematology and Urinalysis.

Individual subject listings of clinical laboratory parameters at each visit will be provided. Values for hematology, serum chemistry, and urinalysis values outside the central laboratory reference ranges will be flagged on the individual subject data listings.

8.3.1 Shift Analysis for Lab Tests

Laboratory abnormalities will be summarized with shift from baseline tables. Each hematology and chemistry value will be flagged as “low”, “normal”, or “high” relative to the normal ranges of the laboratory that performed the assay, or as “unknown” if no results are available. Each urinalysis value will be flagged as “positive”, “negative”, or “unknown” if no values are available.

Shift from baseline to high/low status for hematology and chemistry parameters and shifts from baseline to high/positive for urinalysis will be presented. In each summary, the denominator for the percentage is the number of patients at risk for the shift. The number at risk for a shift to low is the number of subjects whose baseline value was not low and who had at least one post-baseline value. The number at risk for a shift to high is the number of subjects whose baseline value was not high and who had at least one post-baseline value. Subjects will be counted only once for each parameter and each type of shift regardless of how many post-dosing assessments had that type of shift. A shift to high includes normal to high, low to high, and unknown to high; a shift to low includes normal to low, high to low, and unknown to low. A shift to positive includes ‘negative’ to ‘positive’ and ‘unknown’ to ‘positive’.

